## 8.1 ORR Based on iRECIST for Solid Tumors

### 8.1.1 Time Point Tumor Response based on iRECIST

The iRECIST guidelines are based on principles used in RECIST 1.1. The response assigned using iRECIST have a prefix of “i” for assigned responses (e.g., “immune” complete response [iCR]) to differentiate them from responses assigned using RECIST 1.1). The overall responses at each assessment per iRECIST is as the following:

- Complete Response (iCR)
- Partial Response (iPR)
- Stable Disease (iSD)
- Unconfirmed Progressive Disease (iUPD) and Confirmed Progressive Disease (iCPD)
- Not evaluable (NE) = NE

### 8.1.2 Analysis of ORR based on iRECIST

The ORR based on iRECIST is defined as the proportion of subjects whose best overall response is a confirmed iCR or confirmed iPR. The analysis of ORR per iRECIST will be conducted by schedule/dose level for all solid tumors and selected tumor types as appropriate in the All Treated population and Efficacy Evaluable population. The ORR will be estimated with a 95% CI using the exact probability method. The number and percent of subjects with the best overall response of iCR, iPR, iSD, iUPD, iCPD and NE will be summarized. The overall response at each visit along the best overall response based on iRECIST will be presented in a data listing.

### 8.1.3 Derivation of Best Overall Response based on iRECIST

The best overall response based on iRECIST is defined as the best overall response among all post-baseline timepoint assessments until the first iCPD or the last assessment if an iCPD has not been observed. Based on the investigator assessment of overall response at all post-baseline assessments, the best overall response will be determined according to the following:

- iCR > iPR > iSD > iCPD (iUPD if no iCPD) > NE
- iCR = iCR must be confirmed at least 4 weeks later.
- iPR = iPR must be confirmed at least 4 weeks later.
- iSD = at least one iSD or better  $\geq$  49 days after the first dose date and not qualifying for an iCR or iPR. The minimum interval from the first dose date for the best response of iSD is 8 weeks minus 7 days to allow for the visit windows of  $\pm$  7 days (49 days).

- iCPD = iUPD must be confirmed by a subsequent assessment at least 4 weeks later to have iCPD.
- iUPD = iUPD is not confirmed by a subsequent assessment at least 4 weeks later and not qualifying for iSD or better.
- Clinical deterioration will not be considered as documented disease progression.

## 8.2 ORR Based on RECIST 1.1 for Solid Tumors

### 8.2.1 Time Point Tumor Response based on RECIST 1.1

The overall responses at each time point assessment per RECIST 1.1 is derived from the overall response per iRECIST as the following:

- Complete Response (CR) = iCR
- Partial Response (PR) = iPR
- Stable Disease (SD) = iSD
- Progressive Disease (PD) = iUPD or iCPD
- Not evaluable (NE) = NE

### 8.2.2 Analysis of ORR based on RECIST 1.1

The ORR based on RECIST 1.1 is defined as the proportion of subjects whose best overall response before the first PD is a confirmed CR or confirmed PR. The analysis of ORR per RECIST 1.1 will be conducted by schedule/dose level for all solid tumors and selected tumor type as appropriate in the All Treated population and Efficacy Evaluable population. The ORR will be estimated with a 95% CI using the exact probability method. The number and percent of subjects with the best overall response of CR, PR, SD, PD and NE will be summarized. The best overall response based on RECIST 1.1 will be presented in a data listing.

### 8.2.3 Derivation of Best Overall Response based on RECIST 1.1

The best overall response based on RECIST 1.1 is defined as the best overall response among all post-baseline timepoint assessments until the first PD per RECIST 1.1 (the first iUPD per iRECIST) or the last assessment if PD has not been observed. Based on the investigator assessment of overall response at all post-baseline assessments, the best overall response will be determined according to the following:

- CR > PR > SD > PD > NE
- CR = at least two determinations of CR at least 4 weeks apart before progression.
- PR = at least two determinations of PR or better at least 4 weeks apart before progression (and not qualifying for CR).
- SD = at least one SD or better  $\geq$  49 days after the first dose and before progression (and not qualifying for a CR or PR). The minimum interval from the first dose date for the best response of SD is 8 weeks minus 7 days to allow for visit windows of  $\pm$  7 days (49 days).

- Clinical deterioration will not be considered as documented disease progression.

**Table 4. Best overall response when confirmation of CR and PR required.**

Overall response First time point	Overall response Subsequent time point	BEST overall response
CR	CR	CR
CR	PR	SD, PD or PR a
CR	SD	SD provided minimum criteria for SD duration met, otherwise, PD
CR	PD	SD provided minimum criteria for SD duration met, otherwise, PD
CR	NE	SD provided minimum criteria for SD duration met, otherwise, NE
PR	CR	PR
PR	PR	PR
PR	SD	SD
PR	PD	SD provided minimum criteria for SD duration met, otherwise, PD
PR	NE	SD provided minimum criteria for SD duration met, otherwise, NE
NE	NE	NE

CR = complete response, PR = partial response, SD = stable disease, PD = progressive disease, NE = not evaluable.

a If a CR is truly met at first time point, then any disease seen at a subsequent time point, even disease meeting PR criteria relative to baseline, makes the disease PD at that point (since disease must have reappeared after CR). Best response would depend on whether minimum duration for SD was met. However, sometimes 'CR' may be claimed when subsequent scans suggest small lesions were likely still present and in fact the patient had PR, not CR at the first time point. Under these circumstances, the original CR should be changed to PR and the best response is PR.

### 8.3 ORR Based on RECIL 2017 for Lymphomas

#### 8.3.1 Response assessment based on RECIL 2017

The response assessment at each assessment per RECIL 2017 is as the following:

- Complete Response (CR)
- Partial Response (PR)
- Minor Response (MR)
- Stable Disease (SD)
- Progressive Disease (PD)
- Not evaluable (NE)

#### 8.3.2 Analysis of ORR based on RECIL 2017

The ORR based on RECIL 2017 is defined as the proportion of subjects whose best overall response is a CR or PR. The analysis of ORR per RECIL 2017 will be conducted in the All Treated population and Efficacy Evaluable population if data warrants. ORR will be estimated with a 95% CI using the exact probability method. The number and percent of subjects with the best overall

response of CR, PR, MR, SD, PD and NE will be summarized. The overall response at each visit along with the best overall response based on RECIL 2017 will be presented in a data listing.

### 8.3.3 Derivation of Best Overall Response based on RECIL 2017

The best overall response is defined as the best overall response among all post-baseline timepoint assessments until the first PD or the last assessment if PD has not been observed. Based on investigator assessment of overall response at all post-baseline assessments, the best overall response will be determined as the following:

- CR > PR > MR > SD > PD > NE
- CR = at least one CR
- PR = at least one PR or better (and not qualifying for CR).
- SD = at least one SD assessment (or better)  $\geq$  49 days after the first dose (and not qualifying for a CR or PR). The minimum interval from the first dose date for the best response of SD is 8 weeks – 7 days to allow for visit windows of  $\pm$  7 days (49 days).
- Clinical deterioration will not be considered as documented disease progression.

## 8.4 Clinical Benefit Rate

The CBR based on iRECIST is defined as the proportion of subjects whose best overall response is a confirmed iCR, confirmed iPR or iSD of  $\geq$  16 weeks, where iSD  $\geq$  16 weeks is defined as at least one iSD or better for  $\geq$  15 weeks (16 weeks with 1 week visit window) and not qualifying for a confirmed iCR or iPR as the following:

Response at week 8 assessment	Response at week 16 assessment	Response at week 24 assessment	iSD $\geq$ 16 weeks
iSD	iSD/iPR/iCR	Any	Yes
iSD	iUPD	iSD/iPR/iCR	Yes
iSD	iUPD	iUPD/iCPD/NE/missing	No
iSD	NE/missing	iSD/iPR/iCR	Yes
iSD	NE/missing	iUPD/NE/missing	No
iCR/iPR/iSD/iUPD/NE	iSD	Any	Yes

The CBR based on RECIST 1.1 is defined as the proportion of subjects whose best overall response is a confirmed CR, confirmed PR or SD of  $\geq$  16 weeks until the first PD, where SD  $\geq$  16 weeks is defined as at least one SD or better for  $\geq$  15 weeks (16 weeks with 1 week visit window) before the first PD and not qualifying for a confirmed CR or PR as the following:

Response at week 8 assessment	Response at week 16 assessment	Response at week 24 assessment	SD $\geq$ 16 weeks
SD	SD/PR/CR	Any	Yes

SD	PD	Any	No
SD	NE/missing	SD/PR/CR	Yes
SD	NE/missing	PD/NE/missing	No
CR/PR/SD/NE	SD	Any	Yes

The analysis of CBR will be conducted by schedule/dose level for all solid tumors and selected tumor types as appropriate in the All Treated population and Efficacy Evaluable population. The CBR will be estimated with a 95% CI using the exact probability method.

## 8.5 Time to Response

TTR based on iRECIST is defined as the time from the first dose until the first documentation of a subsequently confirmed objective response (confirmed iCR or confirmed iPR). Only subjects who have achieved objective response will be evaluated for TTR.

TTR based on RECIST is defined as the time from the first dose until the first documentation of a subsequently confirmed objective response (confirmed CR or confirmed PR). Only subjects who have achieved objective response will be evaluated for TTR.

TTR based on RECIL 2017 is defined as the time from the first dose until the first documentation of an objective response (CR or PR). Only subjects who have achieved objective response will be evaluated for TTR.

If data warrants, the median and quartiles of TTR and their 95% CIs will be assessed using the Kaplan-Meier method and Brookmeyer and Crowley (1982) method, respectively, and TTR will be presented in a data listing.

## 8.6 Duration to Response

DOR based on iRECIST is defined as time from the date of initial response (iCR or iPR confirmed at least 28 days later) to the date of first documented disease progression that is confirmed or death, whichever occurs first. Only subjects who have achieved objective response (confirmed iCR or confirmed iPR) will be evaluated for DOR. The censoring guidance and the date of PD/death or censoring are same as that for PFS in Section 8.9.1.

DOR based on RECIST 1.1 is defined as time from the date of the first CR or PR (confirmed at least 28 days later) to the date of first documented disease progression (confirmed or not) or death, whichever occurs first. Only subjects who have achieved objective response (confirmed CR or confirmed PR) will be evaluated for DOR. If a disease progression does not occur, DOR will be censored as of the date of their last evaluable disease assessment. The censoring guidance and the date of PD/death or censoring are same as that for PFS in Section 8.9.2.

DOR based on RECIL 2017 is defined as time from the date of the first CR or PR to the date of first documented disease progression (confirmed or not) or death, whichever occurs first. Only

subjects who have achieved objective response (CR or PR) will be evaluated for DOR. If a disease progression does not occur, DOR will be censored as of the date of their last evaluable disease assessment. The censoring guidance and the date of PD/death or censoring are same as that for PFS in Section 8.9.3.

If data warrants, the median and quartiles of DOR and their 95% CIs will be assessed using the Kaplan-Meier method and Brookmeyer and Crowley (1982) method, respectively, and the DOR will be presented in a data listing.

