
Dose Escalation and Dose Expansion To explore additional measures of anti-tumor activity of SL-279252
	
 Duration of response (DOR): time between first response (iCR or iPR, whichever is recorded first) and date of disease progression) Time to response (TTR): time from the start of treatment with SL-279252 to the first objective tumor response (iCR or iPR, whichever is recorded first) Progression free survival: time from first dose of SL-279252 to progression or death, whichever comes first Overall survival: time from first dose of SL-279252 to death

Dose Escalation and Dose Expansion : To explore relationship between PK/pharmacodynamics and the relationship between PK and clinical activity including tumor growth kinetics
	PK/pharmacodynamics and clinical activity outcomes as described above

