8.1.2 Response and Stable Disease Duration

Response duration will be measured from the time measurement criteria for iCR/iPR (whichever is first recorded) are first met until the first date that recurrent or progressive disease is objectively documented, taking as reference the smallest measurements recorded on study (including baseline). Stable disease (SD) duration will be measured from the time of start of treatment until

the criteria for progression are met, taking as reference the smallest sum on study (including baseline).

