**Table 6. Summary of Censoring Guidelines for PFS based on RECIST1.1**

Situation	Date of PD/Death or Censoring	PFS Outcome
Documented PD or death	Date of the first PD or death, whichever comes first	Event (unless the censoring rule specified below)
Death or PD immediately after $\geq 2$ consecutive missed or non-evaluable disease assessments  as per the protocol specified assessment schedule	Date of last evaluable disease assessment prior to missed or non-evaluable assessments, or the first dose of investigational product, whichever occurred last	Censored
No PD or death at time of analysis or lost to follow-up	Date of last evaluable disease assessment	Censored
No tumor assessment at baseline OR No tumor assessment post-first dose, and no death prior to second scheduled post-baseline disease assessment	Date of first dose	Censored

 Two or more consecutive assessments is defined as  $\geq 16+1$  weeks for the first 6 months or  $\geq 24+1$  weeks for 6-24 months (two disease assessments as per protocol plus a one week visit window to allow for a late assessment) after the last evaluable post-baseline disease assessment. If a subject has two or more consecutive missed or non-evaluable assessments followed by an assessment showing no radiologic disease progression, then the assumption will be that the subject did not progress during the missed or non-evaluable assessments.

The median and quartiles of PFS and their 95% CIs will be assessed using the Kaplan-Meier method and Brookmeyer and Crowley (1982) method, respectively. The proportion of subjects that are progression free and alive at 12, 24, 48, 72, 96 weeks and other timepoints of interest and associated 95% CI will be estimated using the Kaplan-Meier method.

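### SAP 8.6 contradicts itself on death without progression in duration of response (RECIST 1.1 and RECIL 2017): an event by definition and by Table 6, but censored by one sentence read literally

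*SAP*

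**What the plan says.** **Protocol.** Section 2 (Table 4) gives, among the exploratory outcomes, "Duration of response (DOR): time between first response (iCR or iPR, whichever is recorded first) and date of disease progression". Section 8.1.2 measures response duration "until the first date that recurrent or progressive disease is objectively documented". Neither mentions death. The same cell of Table 4 does name it for PFS: "Progression free survival: time from first dose of SL-279252 to progression or death, whichever comes first".

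**SAP 8.6, definitions.** Death ends DOR under all three criteria. For iRECIST, DOR runs "to the date of first documented disease progression that is confirmed or death, whichever occurs first". For RECIST 1.1 and RECIL 2017 the end point is "first documented disease progression (confirmed or not) or death, whichever occurs first".

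**SAP 8.6, censoring.** The RECIST 1.1 and RECIL paragraphs, but not the iRECIST paragraph, add: "If a disease progression does not occur, DOR will be censored as of the date of their last evaluable disease assessment". The next sentence in each says that DOR follows the PFS censoring rules (8.9.2 for RECIST 1.1, 8.9.3 for RECIL).

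**The rules referred to.** Table 6, in 8.9.2, counts the earlier of progression and death as an event. It reserves censoring at the last evaluable assessment for "No PD or death at time of analysis or lost to follow-up". Section 8.9.3 applies the Table 6 rules to lymphoma. Table 5, for iRECIST, also makes death an event. Both tables censor a death or progression that comes directly after two or more missed or non-evaluable assessments.

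**SAP Section 12** lists two changes from the protocol, both about analysis populations. The addition of death to DOR is not among them.

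**The concern.** A responder who dies without progression meets two instructions in the same paragraph. The definition counts the death as an event. The censoring sentence asks only whether progression occurred and, since it did not, sends the subject back to the last scan as censored.

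The choice matters because death rules out any later progression. Censoring it lets Kaplan-Meier treat the response as though it might have continued, and the estimate becomes time to progression as if death did not occur. From the date of each such death onward, the curve lies higher than it would with the death counted.

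Because the sentence is missing from the iRECIST paragraph, a literal reading could also split the solid-tumor results. One death would be an event in Table 14.2.5 (iRECIST) and censored in Table 14.2.6 (RECIST 1.1). Figure 14.2.4 is planned to show both DOR analyses. The trial is open-label, so the choice between the two readings is better fixed in the text than made once responders' outcomes are known.

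**Working it through.** The plan states no assumed DOR, event count or precision, so there is no figure to reproduce. The check is first of the text and then of size.

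**Text: a responder who dies without progression and with no missed scans**

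| Source | Treatment of the death |
|---|---|
| Protocol Table 4, synopsis, 8.1.2 | Not addressed |
| SAP 8.6 definition, all three criteria | Event |
| SAP 8.6 added sentence, RECIST 1.1 and RECIL only | Censored, if read literally |
| SAP Table 5 (iRECIST) | Event |
| SAP Table 6 (RECIST 1.1; RECIL through 8.9.3) | Event |

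The introductory text of 8.9.1, 8.9.2 and 8.9.3 also describes censoring of subjects without progression and does not mention death. A programmer who follows the cross-reference therefore meets the same incomplete wording before reaching the table.

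**Size: model and formula.** Assume constant hazards λp for progression and λd for death without progression, and let s = λd/(λp + λd).

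- Median with death as an event: ln 2/(λp + λd).
- Kaplan-Meier median with death censored at the death date: ln 2/λp.
- Ratio: (λp + λd)/λp = 1/(1-s).

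The documents give no value for s. The range 5% to 30% and the 8.0-month median are assumptions.

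| s | 1/(1-s) | 8.0 months becomes | Simulated median, event vs censored (6,000 responders per row) |
|---|---|---|---|
| 5% | 1.05 | 8.4 | 8.0 vs 8.5 |
| 10% | 1.11 | 8.9 | 7.8 vs 8.7 |
| 20% | 1.25 | 10.0 | 8.2 vs 10.3 |
| 30% | 1.43 | 11.4 | 8.1 vs 11.8 |

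The simulated medians agree with the formula within sampling error.

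**Against sampling error.** Take assumed hazards of 5% per month for progression and 2% for death, so s = 2/7 = 29%. The six-month proportion still in response is exp(-0.07 × 6) = 0.657 with death as an event and exp(-0.05 × 6) = 0.741 with death censored, a difference of 0.084. With an assumed 8 responders the binomial standard error is √(0.657 × 0.343/8) = 0.168, so the shift is 0.5 standard errors. With 12 responders it is 0.137, and the shift is 0.6.

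**Small-number illustration (invented data).** Five responders have times of 4, 6, 7, 9 and 12 months, and the 6-month event is a death.

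- Death as an event: the curve goes 0.8, 0.6, 0.4, so the median is 7 months.
- Death censored at a last scan at 5.5 months: 0.8 at month 4, then 0.8 × 2/3 = 0.533 at month 7, then 0.533 × 1/2 = 0.267 at month 9. The median is 9 months.

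**The case against.** The strongest reply is that the SAP settles the matter in its next sentence. Section 8.6 adopts the PFS rules, and Table 6 both makes death an event and limits last-assessment censoring to subjects with neither progression nor death. On that view the added sentence is a shortened form of the Table 6 row, and a programmer working from the definition and the table would never censor the death. This largely stands: it is the better reading, and overstatement is conditional. It does not clear the sentence. That sentence states a rule, appears in two paragraphs and contradicts the definition just before it. The SAP also does not say whether text or table prevails.

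Four stronger readings might be inferred, and the documents do not support them:

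- *That there are three competing treatments of death.* The protocol's DOR definition is silent on death. It differs from the SAP's but sets no third rule.
- *That DOR will be overstated.* This follows only if the sentence is applied against both the definition and Table 6.
- *That one subject could be an event under iRECIST and censored under RECIL.* iRECIST is for solid tumors and RECIL for lymphoma, so no subject is in both. The possible split is between iRECIST and RECIST 1.1.
- *That the lymphoma estimates are much at risk.* The planned DOR tables and Kaplan-Meier figure cover solid tumors only. Lymphoma DOR appears in the output list only as Listing 16.2.6.11.

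**Conclusion.** The sentence is wrong as written in the RECIST 1.1 and RECIL paragraphs of SAP 8.6, and the impact is low. The SAP's definition and its adopted table agree that death without progression is an event, subject to the missed-assessment rule. One sentence, read literally, says otherwise.

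If that sentence were followed, the median would be inflated by about 5% to 43%. This rests on constant hazards, censoring at the death date and an assumed 5% to 30% share of deaths among first events. In the worked case with 8 or 12 assumed responders, the six-month shift is about half a standard error, although with so few responders a single reclassified death can move the median.

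DOR is exploratory, is summarised by Kaplan-Meier only if data warrant, and drives no decision rule. No primary conclusion is affected. Separately, the SAP adds death to the protocol's DOR definition without recording it as a change.

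**What to change.** 1. In the RECIST 1.1 and RECIL paragraphs of SAP 8.6, reword the sentence so that it censors at the last evaluable assessment only *if neither disease progression nor death occurs*. Alternatively, delete it and rely on Table 6.
2. Make the matching edit in 8.9.1, 8.9.2 and 8.9.3, so that the text on censoring subjects without progression also requires that they have not died.
3. Leave the missed-assessment censoring row in Tables 5 and 6 as it is. It is a separate and deliberate rule.
4. Add an entry to SAP Section 12 stating that death is counted as a DOR event and that the protocol definition does not mention it.

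The cost is a few phrases in the SAP and no new data. If the programs already follow Table 6, no result changes. The protocol need not be amended: under Protocol 13.2 an amendment would require IRB/IEC review, and the Section 12 entry is enough.

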## 8.7 Change from Baseline in Tumor Size

For response assessment based on iRECIST for solid tumors, the percent change from baseline in target lesion sum of diameters will be presented by subject using spider plots. The percent change from baseline will only be calculated when all target lesions at baseline are also present and measurable at a post baseline visit. The best percent change from baseline in target lesion sum of diameters is defined as the largest reduction or smallest increase (in the case where a reduction does not occur) from baseline observed over all post-baseline disease assessments up to and including the first PD. The best percent change from baseline will be presented using a waterfall plot.

For response assessment based on RECIL 2017 for lymphoma, the percent change from baseline in target lesion sum of diameters will be presented by subject using spider plots if data warrants. The best percent change from baseline in target lesion sum of longest diameters is defined as the largest reduction or smallest increase (in the case where a reduction does not occur) from baseline observed over all post-baseline disease assessments up to and including the first PD. The best percent change from baseline will be presented using a waterfall plot if data warrants.

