16.6 RECIST 1.1 and iRECIST Criteria

16.6.1 RECIST 1.1 Criteria

Measurable disease: Measurable tumor lesions (nodal, subcutaneous, lung parenchyma, solid organ metastases) are defined as those that can be accurately measured in at least one dimension (longest diameter to be recorded) as ≥ 10 millimeter (mm) with CT scan or clinical examination. Bone lesions are considered measurable only if assessed by CT scan and have an identifiable soft tissue component that meets these requirements (soft tissue component ≥ 10 mm by CT scan). Malignant lymph nodes must be ≥ 15 mm in the short axis to be considered measurable; only the short axis will be measured and followed. All tumor measurements must be recorded in mm (or decimal fractions of cm). Previously irradiated lesions are not considered measurable unless progression has been documented in the lesion.

Malignant lymph nodes: pathological nodes must meet the criterion of a short axis of ≥ 15 mm by CT scan and only the short axis of these nodes will contribute to the baseline sum. All other pathological nodes (those with short axis ≥ 10 mm but < 15 mm) should be considered non-target lesions. Nodes that have a short axis < 10 mm are considered non-pathological and should not be recorded or followed.

Non-measurable disease: All other lesions (or sites of disease), including small lesions (longest diameter < 10 mm [< 1 cm] or pathological lymph nodes with ≥ 10 to < 15 mm [≥ 1 to < 1.5 cm] short axis), are considered non-measurable disease. Bone lesions without a measurable soft tissue component, leptomeningeal disease, ascites, pleural/pericardial effusions, lymphangitis cutis, inflammatory breast disease, lymphangitic involvement of lung or skin, and abdominal masses followed by clinical exam are all non-measurable. Lesions in previously irradiated areas are non-measurable, unless progression has been demonstrated.

Note: Cystic lesions that meet the criteria for radiographically defined simple cysts should not be considered as malignant lesions (neither measurable nor non-measurable) since they are, by definition, simple cysts.

‘Cystic lesions’ thought to represent cystic metastases can be considered as measurable lesions, if they meet the definition of measurability described above. However, if non-cystic lesions are present in the same participant, these are preferred for selection as target lesions.

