Target lesions: When more than one measurable tumor lesion is present at baseline all lesions up to a maximum of 5 lesions in total (and a maximum of 2 lesions per organ), representative of all involved organs, should be identified as **target lesions** and recorded and measured at baseline. Target lesions should be selected on the basis of their size (lesions with the longest diameter), be representative of all involved organs, but in addition should be those that lend themselves to reproducible repeated measurements. It may be the case that, on occasion, the largest lesion does not lend itself to reproducible measurement in which circumstance the next largest lesion which can be measured reproducibly should be selected. A sum of the diameters (longest for non-nodal lesions, short axis for nodal lesions) for all target lesions will be calculated and reported as the baseline sum diameters. If lymph nodes are to be included in the sum, then only the short axis is

added into the sum. At baseline, the sum of the target lesions (longest diameter of tumor lesions plus short axis of lymph nodes: overall maximum of 5) is to be recorded.

After baseline, a value should be provided on the eCRF for all identified target lesions for each assessment, even if very small. If extremely small and faint lesions cannot be accurately measured but are deemed to be present, a default value of 5 mm may be used. If lesions are too small to measure and indeed are believed to be absent, a default value of 0 mm may be used. The baseline sum diameters will be used as reference to further characterize any objective tumor regression in the measurable dimension of the disease.

Non-target lesions: All non-measurable lesions (or sites of disease) plus any measurable lesions over and above those listed as target lesions are considered **non-target lesions** and should also be recorded at baseline. Measurements of these lesions are not required, but the presence, absence, or in rare cases unequivocal progression of each should be noted throughout follow-up.

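### SAP 8.7 gives no tumor-size change at a visit where a target lesion has disappeared, so the solid-tumor waterfall and spider plots understate the deepest responses

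*SAP*

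**What the plan says.** SAP Section 8 lists change in target-lesion size among the efficacy endpoints. SAP 8.7 sends the by-visit percent change to spider plots and the best percent change to a waterfall plot (Figures 14.2.3 and 14.2.2). For solid tumors it adds a condition: the value is to "only be calculated when all target lesions at baseline are also present and measurable at a post baseline visit". The lymphoma paragraph of 8.7 has no such condition.

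Protocol 16.6.1 asks sites to enter a value for each target lesion at each assessment after baseline, however small. It allows 5 mm for a lesion that is present but cannot be measured accurately. For the other case it says: "If lesions are too small to measure and indeed are believed to be absent, a default value of 0 mm may be used".

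Nothing in the SAP bridges the two. SAP 5.2.2 makes the change missing if either value is missing, SAP 8.11.2 makes no imputation for efficacy variables beyond the handling of NE, and SAP Section 12 lists no departure from the protocol here.

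On the time span, SAP 8.7 defines the best change as the largest reduction or smallest increase "from baseline observed over all post-baseline disease assessments up to and including the first PD". SAP 8.2.1 maps "Progressive Disease (PD) = iUPD or iCPD", and SAP 8.2.3 treats the first PD as the first iUPD. By contrast, iRECIST best overall response in SAP 8.1.3 runs "until the first iCPD or the last assessment if an iCPD has not been observed".

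**The concern.** The condition fails in the very situation that the plots are meant to show. Complete response in Protocol 16.6.2 requires target lesions to disappear, and a lesion that has disappeared is not present. A programmer who follows the text leaves that visit blank, although the protocol supplies a number for it. The loss falls mainly on shrinkage, so the figures would tend to understate activity and could disagree with the response table beside them.

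Protocol 3.3.2 names anti-tumor activity among the inputs to the RP2D. An expansion cohort has at most 15 subjects and some dose levels may have a single subject, so one truncated or missing bar would be visible.

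**Working it through.** The documents give no figure to reproduce. The inputs are:
- the percent-change formula, 100 x (post - baseline) / baseline (SAP 5.2.2);
- the condition in SAP 8.7;
- the 0 mm and 5 mm values in Protocol 16.6.1;
- the response thresholds in Protocol 16.6.2;
- lesion sizes, which are assumed for illustration.

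**Step 1: a regressing subject.** Baseline lesions 40 + 25 = 65 mm.

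| Visit | Lesions (mm) | Change with protocol values | SAP 8.7 as written |
|---|---|---|---|
| Week 8 | 24 + 12 = 36 | (36 - 65)/65 = -44.6% | calculated |
| Week 16, second lesion absent | 20 + 0 = 20 | (20 - 65)/65 = -69.2% | no value |
| Week 16, second lesion faint instead | 20 + 5 = 25 | (25 - 65)/65 = -61.5% | no value, unless the 5 mm entry counts as a measurement |
| Week 16, second lesion measured at 6 mm instead | 20 + 6 = 26 | (26 - 65)/65 = -60.0% | depends on how measurable is read |
| Week 24, both absent | 0 + 0 = 0 | -100% | no value |

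With the second lesion absent at week 16, the waterfall bar is -44.6% under the SAP rule and -100% with the protocol's values, a gap of 55.4 percentage points. The spider line stops at week 8. Had a lesion already gone at the first scan, with no later visit qualifying, the subject would have no bar.

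**Step 2: how far the reading of measurable matters.** If the word imports the baseline limits of Protocol 16.6.1 (10 mm, or 15 mm short axis for nodes), the largest reduction that can be plotted for a single lesion of baseline size B is:
- non-nodal, 1 - 10/B: 33.3% for 15 mm, 50% for 20 mm, 75% for 40 mm. A 30% reduction needs B of at least 10/0.7 = 14.3 mm.
- nodal, 1 - 15/B: 25% for 20 mm, 50% for 30 mm. A 30% reduction needs B of at least 15/0.7 = 21.4 mm.

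If measurable means only that the lesion can be measured, these ceilings disappear. What is left is the loss of visits with absent lesions and, arguably, faint ones.

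**Step 3: direction.** Baseline 12 + 30 = 42 mm becomes 0 + 50 = 50 mm: (50 - 42)/42 = +19.0%. This visit is also blocked, so the loss is not confined to shrinkage.

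**Step 4: the progression cut.** Take a subject whose first scan is iUPD on target growth. The sum is then at least 20% above baseline, since baseline is the nadir. If the subject later reaches a confirmed iPR, the sum is at least 30% below baseline. With the cut at first iUPD the bar is +20% or more; with the cut at first iCPD it is -30% or lower. The subject is a responder in the iRECIST ORR in both cases.

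**The case against.** The best defence is that the condition was meant to exclude incomplete sums, where a target lesion was not imaged or could not be evaluated, and that a sensible programmer would accept recorded 0 mm and 5 mm entries as valid. That is plausible, but the text does not say it, and the word only leaves no room for it.

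Four stronger conclusions might be inferred, and the documents do not support them:
- **Any lesion that falls below 10 mm (or a node below 15 mm) loses its value.** Protocol 16.6.1 uses those limits to qualify target lesions at baseline. For follow-up it asks for a value even for very small lesions, and Protocol 16.6.2 has nodes recorded even below 10 mm. The ceilings in Step 2 are therefore conditional on one reading.
- **The best responders vanish from the plots.** The rule blocks a visit, not a subject. An earlier qualifying visit leaves an understated bar.
- **Only shrinkage is ever removed.** Step 3 shows otherwise, and visits with unassessed lesions are dropped too, whatever the response.
- **A subject with iUPD followed by iPR shows only growth.** Shrinkage before the iUPD still counts, iUPD may come from new or non-target lesions, and the spider plot has no progression cut.

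It is also fair that tumor-size change is absent from the objectives tables of both documents, that no passage says these figures are read in the RP2D review, and that a first-PD cut would match the planned RECIST 1.1 response tables. These points limit the weight of the matter; they do not remove the conflict with Protocol 16.6.1.

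**Conclusion.** The concern stands in limited form. As written, SAP 8.7 withholds the percent change at any solid-tumor visit where a target lesion has disappeared. Complete disappearance of all target lesions can therefore never be plotted, and the deepest responses are understated. This conclusion rests only on the ordinary meaning of present. Any further loss for small lesions depends on how measurable is read, which the SAP leaves open.

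The number of subjects affected cannot be derived from the documents; the 55.4-point gap belongs to one assumed subject. The effect is confined to Figures 14.2.2 and 14.2.3. ORR, CBR and PFS rest on response assessments rather than on this variable, and the lesion measurements and sums are still listed.

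The progression cut is a secondary point. If first PD means first iUPD, as SAP 8.2.3 has it, shrinkage after an iUPD that is never confirmed counts in the iRECIST ORR but is left out of the waterfall bar.

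**What to change.** Replace the solid-tumor condition in SAP 8.7 with wording such as: Percent change is calculated at every visit where all baseline target lesions were assessed, using the recorded measurement however small, 0 mm for lesions believed absent, and 5 mm for lesions present but too small or faint to measure accurately (Protocol 16.6.1); it is missing only if a target lesion was not assessed or not evaluable. Because the protocol permits these two values rather than requiring them, the SAP should say that they are applied in the derivation when the site records the lesion's status without a number.

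State the cut for the iRECIST waterfall as the first iCPD, and label any version cut at first PD as RECIST 1.1.

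The cost is SAP wording and programming. No new data are needed, provided that the eCRF separates an absent lesion from one not assessed.
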